8.1 Hypotheses and Objectives

8.1.1 Objectives

8.1.1.1 Efficacy Objective

To evaluate the efficacy of etrasimod in patients with PG over a 12-week treatment period.

8.1.1.2 Safety Objective

To assess the safety and tolerability of etrasimod in patients with PG over a 12-week treatment period.

8.1.2 Hypotheses

There are no formal hypothesis tests specified in this open-label study due to the lack of control treatment group.

8.2 Sample Size and Power Calculations

There is no formal sample size estimation for this proof-of-concept open label study. A sample size of 8 subjects is reasonable to assess proof-of-concept of the efficacy of etrasimod in the target population.

8.3 Analysis Populations

Efficacy endpoints will be analyzed in enrolled patients who have baseline and at least 1 post-baseline measure.

Safety endpoints will be analyzed in enrolled patients who received at least 1 dose of the study drug.

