3 INVESTIGATIONAL PLAN

3.1 Overall Study Design and Plan

This is a Phase 2a, open label, proof-of-concept clinical study to assess the efficacy and safety of etrasimod (APD334) in patients with PG. The trial will include adult patients, 18-80 years of age with active PG ulcers.

All visits in the study are ambulatory visits. The screening period will last up to 4 weeks and will be followed by a 12-week treatment period. During the treatment period, patients will need to take 1 tablet of study medication once per day. The last dose is planned to be taken one day before the end of the treatment period at Week 12. A follow-up visit will take place 2 weeks after the end of treatment.

Figure 1 Study Design

The study will consist of the following periods:

Screening Period (up to 4 weeks before baseline visit):

Each patient will be asked to visit the study site for screening assessments within 4 weeks prior to the planned start of the treatment (Day 1). All patients must be consented before any study specific procedure is performed and written informed consent must be obtained. Patients will then undergo screening procedures to determine eligibility.

[REDACTED]

Treatment Visits:

Baseline Visit (Day 1): Patients will return to the study site to receive the first dose of the study medication. Patients should be instructed to take their tablet as a first thing in the morning on an empty stomach. Patients should be advised not to crush, break, chew, or dissolve the tablet and to take study medication with water. The patients will remain at the study site for at least 6 hours for safety evaluation (please refer to the [REDACTED])

[REDACTED]

Visits Week 2, Week 4, Week 8, and Week 12: Patients will return to the study site and perform all planned examinations as described in [REDACTED]. Last dose of study medication is planned 1 day before the end of the treatment visit at Week 12.

Follow up Visit/End of Study Visit:

[figure not shown]
Visit Week 14, 2 weeks after end of treatment: Patients will return to the study site for the final visit, and final procedures will be performed per [REDACTED]

[figure not shown]
Premature Discontinuation: All procedures planned for Week 12 visit should be performed for all patients that discontinue the study prematurely.

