6.13.1 Permitted medications for the treatment of pyoderma gangrenosum and associated conditions

The following concomitant medication are allowed provided that the dose has been stable for at least 2 weeks prior to baseline and remain stable throughout the study:

- Oral corticosteroids (maximal allowed prednisone ≤ 20 mg/day, or equivalent)
- TNF-alpha inhibitor (etanercept, infliximab, adalimumab or other)
- Oral 5-ASA medication (for patients with ulcerative colitis)
- Antidiarrheal treatment
- OTC analgesics (paracetamol / acetaminophen, NSAIDs)

In addition, topical medication (other than excluded medication) that the patient is receiving at baseline should be continued, provided that these are stable for 2 weeks prior to baseline and should remain stable throughout the study.

Only non-sticking dressing of the wounds (e.g., jelonet and compression bandages) could be used throughout the study period.

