6.14 Removal of Patients from the Trial or Study Drug

Patients experiencing a significant infection (as judged by the investigator) will be discontinued from the study drug immediately.

The study may be terminated early if, in the opinion of the sponsor, investigator, or IEC, an unacceptable risk to the safety and welfare of patients is posed by the continuation of the study in light of review of the key safety data.

Patients will be free to withdraw from the study at any time should they so wish. A patient may be withdrawn from the study for any of the following reasons (including but not limited to):

- Clinical investigator may remove a patient if, in his/her opinion, it is in the best interest of the patient.
- Withdrawal of consent - Any patient may withdraw his/her consent from the study at any time. The investigator should make a reasonable attempt to document the specific reason why consent was withdrawn.
- Deviation/noncompliance with the protocol or study drug (<80%).
- An AE.
- Lost to follow up.

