6.14.1 Handling of Withdrawals

Although a patient is not obliged to give his/her reason for withdrawing prematurely, the investigator will make a reasonable effort to obtain the reason while fully respecting the patient's rights. If there is a medical reason for withdrawal, the patient will remain under the supervision of the study physician until in satisfactory health. Reasonable efforts will be made to contact a patient who fails to attend any follow-up appointments, in order to ensure that he/she is in satisfactory health.

If a patient is prematurely discontinued from this study, every attempt will be made to follow the Week 12 procedures. If consented by the patient, effort will be made to conduct a follow-up visit within 2 weeks of discontinuation [REDACTED] if the patient has received at least 1 dose of the study drug.

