6.14.2 Replacements

Patients who terminate early from the study will not be replaced.

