8.5 Efficacy Endpoints

As this is proof-of-concept study all endpoints will be exploratory. The efficacy endpoints will be as follows:

- change from baseline (Day 1 pre-dose) to Week 12 in Physician Global Assessments for active skin manifestations.

Assessment of target lesion/ulceration

- 0: Total resolution of target ulcer with no signs of active PG*
- 1: almost completely healed target ulcer with only minimal signs of active PG*
- 2: Evidence of target ulcer healing which involves at least 50% of ulcer/ulcer margin*
- 3: Evidence of target ulcer healing which involves less than 50% of ulcer/ulcer margin*
- 4: No evidence of target ulcer healing*

- change from baseline (Day 1 pre-dose) to Week 12 in Patient Global Assessments for active skin manifestations: Visual Analog Scale (VAS) for assessment of severity of the disease and severity of pain by patient.
- change from baseline (Day 1 pre-dose) to Week 12 in Dermatology Life Quality Index (DLQI) (to measure how much a patient's life is affected through their skin problems)
- change from baseline (Day 1 pre-dose) to Week 12 in CRP levels

In addition, the following measures will be assessed as per Schedule of Procedures and Visits:

- Imaging (digital photos) of the target lesion.
- Evaluation of the changes in surface area of target lesion.
- Skin punch biopsies (if performed).

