8.6 Statistical Methods

8.6.1 Efficacy Analysis

There are no inferential comparisons for study endpoints. Summary statistical analyses will be performed for all efficacy measures. For proportion based measures, N, frequencies, proportion and its 95% confidence interval (CI) will be produced. For continuous measure, N, mean, median, range, and SD will be produced for observed values, and additional 95% CI for change or percent change from baseline will be produced if applicable.

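### Does the plan need to say whether assessments made at premature discontinuation count as Week 12 values?

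*Combined protocol and SAP*

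**What the plan says.** Section 8.3 admits a patient to the efficacy analyses on the strength of a baseline and a single later value: "Efficacy endpoints will be analyzed in enrolled patients who have baseline and at least 1 post-baseline measure". Section 8.5 lists changes in the physician global assessment (PGA), the patient VAS scores, the DLQI and CRP, all to Week 12. The first reads "change from baseline (Day 1 pre-dose) to Week 12 in Physician Global Assessments for active skin manifestations".

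Two sections cover patients who stop early. Section 3.1 says "All procedures planned for Week 12 visit should be performed for all patients that discontinue the study prematurely", and Section 6.14.1 says "If a patient is prematurely discontinued from this study, every attempt will be made to follow the Week 12 procedures". Section 6.14.2 adds: "Patients who terminate early from the study will not be replaced".

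Section 8.6.1 is purely descriptive: "For continuous measure, N, mean, median, range, and SD will be produced for observed values", with a 95% CI for change or percent change where applicable. Section 8 leaves the details to a separate SAP, to be final before database lock, and says that confidence intervals serve non-inferential comparison with historical data. That SAP is not in the text supplied, and the visit schedule is redacted.

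**The concern.** Read together, these sections leave a loose end. A patient who stops at Week 5, say, stays in the efficacy set and has a full set of Week 12 procedures dated Week 5. One analyst might enter those values in the Week 12 row. Another might keep them as an early-termination visit and report Week 12 on fewer patients.

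If the early values are left out, N shows the shortfall. If they are entered, and every stopper was assessed, N still reads 8 and the row silently mixes assessment times. With 8 patients and no replacement, one or two stoppers can visibly move a mean that is meant to be set beside historical data. If patients tend to stop because they are not improving, the version that leaves them out looks better.

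**Working it through.** The plan gives no figure to reproduce. Section 8.2 states 8 patients without a formal calculation, and no SD, effect size or dropout rate appears. The check is therefore how far apart the two readings can be, and which one the text supports.

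**Inputs.** N = 8 (Section 8.2) and a PGA score from 0 to 4 (Section 8.5). Assumed: k early stoppers, all assessed when they stop; completers' mean change m; stoppers' mean change s.

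**Difference between the readings.**

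- Early values kept apart: mean = m, with n = 8 - k.
- Early values entered as Week 12: mean = [(8 - k)m + ks]/8, with n = 8.
- Second minus first = k(s - m)/8.

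This is zero if nobody stops early or if both groups change equally.

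**Bound.** If every patient starts at 4 (assumed from the non-healing ulcer required in Section 4.1.1), changes lie between -4 and 0. Then |s - m| is at most 4, and the gap is at most 4 × 1/8 = 0.5 point for k = 1 and 4 × 2/8 = 1.0 point for k = 2. Reaching it requires one group to heal completely while the other does not change at all.

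**Stoppers with no change (s = 0).**

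| k | Completers' mean m | Mean with stoppers entered | Gap |
|---|---|---|---|
| 1 | -1.00 | -0.875 | 0.125 |
| 1 | -2.00 | -1.75 | 0.25 |
| 1 | -3.00 | -2.625 | 0.375 |
| 2 | -1.00 | -0.75 | 0.25 |
| 2 | -2.00 | -1.50 | 0.50 |
| 2 | -3.00 | -2.25 | 0.75 |

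**Against the width of the interval.** The t-based 95% half-width is t(0.975, n - 1)/√n × SD, which is 1.049 SD for n = 6 and 0.836 SD for n = 8. The SD cannot be held constant across the two readings, because adding unchanged patients raises it. Take six completers with mean -2 and SD 1.0 (assumed) and two zeros:

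- Sum of squares about the new mean of -1.5: 5 × 1.0² + 6 × 0.5² + 2 × 1.5² = 5 + 1.5 + 4.5 = 11.
- SD = √(11/7) = 1.25.
- Half-width at n = 8: 0.836 × 1.25 = 1.05. For the six completers alone: 1.049 × 1.0 = 1.05.

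The 0.50 gap is about half of either half-width.

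Individual assumed scores tell the same story. Six completers at -3, -3, -2, -2, -2, -1 give a mean of -2.17 (95% CI -2.96 to -1.38). Adding two zeros gives -13/8 = -1.625 (95% CI -2.62 to -0.63). The intervals overlap widely.

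**Which reading the text supports.** Section 8.5 sets the endpoint at Week 12, and Section 3.1 makes Week 12 a scheduled visit. Sections 3.1 and 6.14.1 say which procedures a stopper undergoes; they do not rename that visit Week 12. Section 8.6.1 asks for N alongside summaries of observed values, and no carry-forward or relabelling step appears anywhere. The ordinary reading is a summary by scheduled visit with the N available. Section 8.3 does not conflict with this: a stopper can belong to the set, contribute to earlier visits, and have no Week 12 value.

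**The case for a change.** The best case for a change has four parts.

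- A score taken at discontinuation is itself an observed value, so Section 8.6.1 does not strictly say which visit it belongs to. The PGA form in Appendix 2 has rows for fixed weeks only, so such a score could easily be written in the Week 12 row.
- Stopping may be related to outcome. Section 6.13.1 requires permitted background treatment to be "stable for at least 2 weeks prior to baseline and remain stable throughout the study", and Section 6.14 lists protocol deviation among the reasons for withdrawal. A patient whose background treatment changes because the ulcer worsens might therefore leave.
- The SAP need only be final before database lock. In an open-label study, outcomes can be known by then.
- A sentence settling the label would cost almost nothing.

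The first part stands as a matter of wording: nothing supplied rules out the other label. Its practical force is limited, because the PGA form has a column for the date and the actual assessment day can be recovered. The second is an inference. Section 6.14 says a patient may be withdrawn, not must be, and no frequency is given. The third is fair as a general caution, but assigning visits is ordinary SAP content and there is no test whose error rate a late choice could disturb. The fourth is true, yet low cost alone does not make a change necessary. Going further, for instance by counting missing patients as non-responders, would add a rule for a response endpoint that Section 8.5 does not list.

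**Conclusion.** No change to the plan is needed. This is a gap in detail that analysts fill sensibly: summarise by scheduled visit, show n at Week 12, and keep early-termination values identifiable by their actual day. The text already points that way, and the separate SAP or the redacted schedule may state it outright, so an omission from the full plan is not shown.

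For unchanged stoppers and completers averaging -2.00, the two readings differ by 0.25 point with one stopper and 0.50 point with two. The ceilings are 0.5 and 1.0 point if all patients start at 4. The number of stoppers, their changes, the SD and the common baseline are all assumed.

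Nothing formal turns on the difference. The endpoints are exploratory (Section 8.5), no hypothesis is tested (Section 8.1.2), the historical comparison is non-inferential (Section 8), and the text supplied states no threshold that the Week 12 mean must reach.

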| Concurrent Control: | No concurrent control |
| Background | 
Etrasimod is an orally available, selective, sphingosine 1-phosphate (S1P) receptor agonist. S1P is a signaling sphingolipid required by lymphocytes to exit the lymphoid tissue and enter the bloodstream via a chemotactic gradient. The S1P₁ receptor is a physiological mediator which has been shown to regulate lymphocyte recirculation between lymphoid tissue and blood. Binding and internalization of the S1P₁ receptor may result in lymphocyte retention within lymphoid tissue, with subsequent reduction in peripheral lymphocyte count and lymphocyte availability for recruitment to sites of inflammation. S1P₁ receptor surface expression is required for S1P gradient-mediated lymphocyte migration out of lymphoid tissue into the circulation¹.
 
Agonists of the S1P₁ receptor, such as etrasimod, block lymphocyte
 |

| | |
|----------------------------|---|

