Treatment options

The best documented treatments are systemic corticosteroids and cyclosporin A. Combinations of steroids with cytotoxic drugs are used in resistant cases. The combination of steroids with sulfa drugs or immunosuppressants has been used as steroid-sparing modalities. In some cases, anti-TNF therapy was reported to be beneficial which suggests that inhibition of TNF may help.

Gevokizumab is a potent IL-1 beta monoclonal antibody with unique allosteric modulating properties and has the potential to treat patients with a wide variety of inflammatory and other diseases. Gevokizumab binds strongly to interleukin-1 beta (IL-1 beta), a pro-inflammatory cytokine, and modulates the cellular signaling events that produce inflammation. This agent was being developed as a potential treatment for PG but development was discontinued in 2016.

In addition, results from studies for canakinumab, another anti IL-1 β biologic, have been published for this drug ¹³.

[REDACTED] Lymphocyte trafficking agents such as natalizumab and vedolizumab, both injectable or infused therapies, have demonstrated efficacy in IBD indications. More recently, ozanimod, an S1P₁ oral receptor modulator, showed promising results in a Phase 2 study for UC ¹⁴.

The availability of lymphocyte trafficking agents such as etrasimod would offer patients an additional, oral treatment for PG.

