6.13.2 Excluded Medications

The following medications are excluded prior or during the study:

- Exposure to B-cell or T-cell targeted therapies (such as natalizumab, rituximab, abatacept) within 5 half-lives prior to Day 1
- Other immunosuppressive, immunomodulating or antineoplastic agents or other monoclonal antibody / biologic not listed in the Permitted Medications within 5-half-lives prior to Day 1 (small molecules) or 60 days prior to D1 (biologics).
- All live vaccines within 6 weeks prior to Day 1, during study treatment and for at least 6 months after the last dose of study drug
- Moderate to strong inhibitors of CYP2C9 (e.g., amiodarone, felbamate, fluconazole, miconazole, piperine). within 5-half-lives prior to Day 1, during the study and for 2 weeks after the last intake of study medication
- Other routes for systemic corticosteroids (IM and IV)
- Class Ia or Class III anti-arrhythmic agents
- Any other medication which in the opinion of the investigator would affect the suitability of the patient to continue in the study, interfere with interpretation of study results or affect compliance with the protocol requirements
- Receipt of any investigational agent within 30 days or 5 half-lives (whichever is longer), prior to Day 1.

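### No rule covers Week 12 values recorded after PG or PG-pain treatment is added, so gain from that treatment would be read as etrasimod benefit

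*Combined protocol and SAP*

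**What the plan says.** **Analysis.** Section 8.3 gives the efficacy population: "Efficacy endpoints will be analyzed in enrolled patients who have baseline and at least 1 post-baseline measure". Section 8.5 defines four endpoints as change from Day 1 pre-dose to Week 12: PGA (scored 0 to 4), patient VAS for disease severity and for pain, DLQI, and CRP. Lesion surface area is assessed in addition. Section 8.6.1 adds: "Summary statistical analyses will be performed for all efficacy measures". For continuous measures these are statistics on observed values, with a 95% CI for change where applicable. Section 8 says that confidence intervals will be set beside historical data, non-inferentially, and leaves details to a separate SAP to be finalised before database lock. The synopsis records "No concurrent control".

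**Concomitant treatment.** Section 6.13.1 permits listed PG and associated drugs, including OTC analgesics, "provided that the dose has been stable for at least 2 weeks prior to baseline and remain stable throughout the study". Topicals in use at baseline must also stay stable. Section 6.13.2 excludes, among others, other immunosuppressive or immunomodulating agents, IM and IV corticosteroids, and any medication that the investigator thinks would interfere with interpreting the results.

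**Consequences of a change.** Section 6.14 says that a patient may be withdrawn for a protocol deviation. Section 6.14.1 has Week 12 procedures attempted after premature discontinuation. Section 6.14.2 rules out replacement. Section 6.13 has all medications recorded with start and stop dates, where known.

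**The concern.** The rules on concomitant treatment govern conduct; they do not say what happens to a measurement taken after treatment has changed. Patients who do poorly on etrasimod are the ones most likely to be given more PG or pain treatment. Any resulting bias would therefore run mainly in one direction, turning failures into apparent improvement. A concurrent control would show how much improvement comes with added treatment, but this study has none. Its result is meant to inform a proof-of-concept judgement on efficacy, and with eight patients one or two such cases can change the picture.

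**Working it through.** **1. Is there a handling rule?** Read together:
- Section 8.3 sets no condition on concomitant treatment.
- Section 8.5 fixes the time point and does not mention treatment changes.
- Section 8.6.1 summarises observed values.
- No per-protocol set, intercurrent-event strategy or missing-data rule appears.
- A deviating patient may stay in (6.14), and one who leaves is still assessed where possible (6.14.1).

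The analysis as stated therefore includes the observed Week 12 value whatever treatment change came before it.

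**2. Do the medication rules prevent the situation?** In part. Raising a permitted PG drug breaches 6.13.1. Other cases are less clear:
- Starting a topical not in use at baseline is not addressed by name.
- Only OTC analgesics are named; prescription analgesics fall to the investigator-opinion item.
- The Introduction says: "The combination of steroids with sulfa drugs or immunosuppressants has been used as steroid-sparing modalities". Sulfa drugs are named on neither list.
- Corticosteroids are addressed as oral, as IM or IV, and through baseline topicals. Local injection is not named, though the class exclusion of immunosuppressive and immunomodulating agents may cover it.
- That class exclusion stands under a heading that covers the period before or during the study, but its time windows only count back from Day 1.

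**3. Size.** The plan has no figure to reproduce. Section 8.2 says "There is no formal sample size estimation for this proof-of-concept open label study" and then "A sample size of 8 subjects is reasonable to assess proof-of-concept of the efficacy of etrasimod in the target population". It gives no effect size, SD or rescue rate. What follows uses n = 8, all with Week 12 values; every other input is an assumption.

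*Mean change.* If k patients each gain g points because of added treatment, the mean shifts by k × g / 8.
- PGA, k = 1: 1/8 = 0.125 (g = 1) to 4/8 = 0.5 (g = 4).
- PGA, k = 2: 0.25 to 1.0.
- 10 cm VAS, k = 1, g = 2 to 6 cm: 0.25 to 0.75 cm.

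*Proportions.* Each affected patient moves any proportion by 1/8 = 12.5 points. For example, under an assumed definition of improvement, 4/8 = 50.0% (exact 95% CI 15.7% to 84.3%). If two of those four improved only after added treatment, 2/8 = 25.0% (3.2% to 65.1%).

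*Invented PGA data.* Suppose changes without added treatment of 0, 0, 0, 0, −1, −1, −2, −3.
- Mean = −7/8 = −0.875, SD 1.126. With t = 2.365 on 7 df, the 95% CI is −1.82 to 0.07.
- If two of the zeros become −3 after added treatment, the mean is −13/8 = −1.625, SD 1.302, 95% CI −2.71 to −0.54.
- The shift is 2 × 3/8 = 0.75, and the interval no longer contains zero.

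*How likely is it?* If each patient independently has chance q of a treatment change, P(at least one) = 1 − (1 − q)^8.

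| q (assumed) | at least one of 8 | at least two of 8 |
|---|---|---|
| 5% | 33.7% | 5.7% |
| 10% | 57.0% | 18.7% |
| 20% | 83.2% | 49.7% |
| 30% | 94.2% | 74.5% |

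**The case against.** The strongest reply has four parts.

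- **The text is silent; it does not state a rule.** No sentence says that values after added treatment count as benefit, and Section 8 leaves details to a separate SAP. Section 8.7.3 (Concomitant Medication), listed in the contents, is also not in the available text; it sits under safety. This stands as a limit on the claim. It is also why the remedy is timely: the rule can still be written before database lock.
- **The plan already forbids much of this.** A reader might infer that a site is free to raise prednisone for a worsening ulcer, or that only investigator opinion stands in the way of new PG treatment. The documents do not support either reading. Section 6.13.1 requires stable doses, 6.13.2 has a class exclusion as well as the clause on interference with interpretation, deviation is a listed ground for withdrawal, and adherence is monitored (10.3). These rules should make such cases fewer, but they leave the resulting data unhandled.
- **There is no responder endpoint.** A reader might take 25% against 50% as the expected distortion of a response rate. Section 8.5 defines only changes from baseline, so the proportions above need an assumed threshold as well as assumed cases. The mean shift applies directly.
- **Everything is exploratory.** There are no hypothesis tests, and the historical comparison is non-inferential, so no type I error or power figure is affected. With eight patients and dated medication records, affected cases could be picked out individually. That is true, but nothing in the text requires it.

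**Conclusion.** The point holds as a gap in data handling. On the available text, an observed Week 12 value enters the efficacy summaries whatever PG or pain treatment was added before it. In an uncontrolled arm of eight set beside historical data, that improvement cannot be separated from etrasimod's effect, and the likely direction favours the drug.

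The size cannot be derived from the documents. Per affected patient it is g/8 on the mean PGA change, or 12.5 points on any proportion-based summary. How many patients would be affected is unknown.

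The conclusion assumes that the separate SAP does not already contain a rule, and that some treatment changes will occur despite Sections 6.13.1 and 6.13.2. It should be corrected before database lock, but it does not invalidate the study.

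**What to change.** In Section 8.6.1, or in the SAP before database lock:

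1. From the concomitant-medication records, identify patients with an increase in permitted PG therapy, or a new systemic, topical or local PG treatment, after Day 1.
2. Keep the all-observed summary. Beside it, present one in which these patients count as not improved from the date of the change. In any proportion they count as non-improvement. For PGA, lesion, VAS, DLQI and CRP means they are given a change of zero, or the last value before the change if that is worse than baseline. Carrying the last value forward in every case could preserve a transient early gain.
3. For analgesics, apply the rule to the pain VAS only, and only when one was started or increased for PG pain. Use for an unrelated complaint should not cancel a real improvement.
4. List affected patients individually, with the treatment, the date, and values before and after.

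The cost is SAP wording and one extra derivation, with a possibly smaller reported effect. Section 6.13 mentions dates but not dose or reason for use, so the sponsor should confirm that the CRF captures both.

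No change to permitted or excluded treatment is proposed. Separately, the sponsor should reconcile the lists in 6.13.1 and 6.13.2 with the PG treatments named in the Introduction, and make clear which 6.13.2 items apply during the study.
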